^fAdverse Event (AE) check phone call: Patients are contacted approximately 70 days after their last study visit. Only the AE form is completed.

^gPatients randomized to continue adalimumab and patients randomized to stop adalimumab who have a treatment failure and restart will be provided open-label drug until Month 12 (or Month 15 if treatment failure occurs at Month 12).

Form Completion Schedule

After completing each study visit, study coordinators will review the electronic case report forms for completion and accuracy and submit them electronically via REDCap. If study visit data are recorded on hard copies of the forms, these paper copies should be scanned and emailed to the Coordinating Center ([contact]) and kept in a secure location at the site. All US centers are part of the Childhood Arthritis and Rheumatology Research Alliance (CARRA) and submit data to the registry for their JIA patients. As we are collecting similar data on an overlapping patient population, CARRA has allowed us to use their data collection forms. We will collect data using forms developed specifically for ADJUST in addition to several forms from the CARRA registry that are applicable to the study procedures and data collected for this study.

	Baseline	Months 1-4	Month 6	Months 8 & 10	Month 12	Treatment Failure ^a	Additional Visit ^b
Patient Consent Forms	✓						
Eligibility and Screening Form	✓						
Baseline Treatment Assessment Form	✓						
Baseline Demographics Form	✓						
Baseline Ophthalmology Form	✓						
Baseline Rheumatology Form	✓						
Clinical Eye Exam Form	✓	✓	✓	✓	✓	✓	✓
Arthritis Evaluation Form	✓	Month 3	✓		✓	✓	
Visual Acuity Form	✓	✓	✓	✓	✓	✓	✓
OCT Form	✓	✓	✓	✓	✓	✓	✓
Standard of Care Lab Form	✓	Month 3 ^c	✓	Month 8 or 10 ^c	✓	✓	✓ ^b
Research Sample Lab Form	✓		✓		✓	✓	
Adverse Event Checklist	✓	✓	✓	✓	✓	✓	✓ ^d
Quality-of-Life Questionnaires (CHAQ, CVFQ, EYE-Q, EQ-5D-Y)	✓		✓		✓	✓	
Treatment Assessment Form ^e	✓	✓	✓	✓	✓	✓	✓
Medication Adherence Log	✓	✓	✓	✓	✓	✓	✓
Patient Dropout Form (if applicable)		(✓)	(✓)	(✓)	(✓)	(✓)	(✓)

Serious Adverse Event Narrative Form (if applicable)		(✓)	(✓)	(✓)	(✓)	(✓)	(✓)
Protocol Deviation Form (if applicable)	(✓)	(✓)	(✓)	(✓)	(✓)	(✓)	(✓)
Interim Masking Decision Form (if applicable) ^f		(✓)	(✓)	(✓)			(✓)

^aTreatment failure can be declared at any visit, including an unscheduled visit.

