Previous studies have found that between 9.2% and 32% of patients on adalimumab treatment developed antibodies against the drug.⁵⁵⁻⁵⁷ There is evidence to suggest that patients with uveitis who develop adalimumab antibodies may have worse ocular inflammatory outcomes compared to patients without these antibodies.⁵⁶ Furthermore, preliminary data on discontinuation of anti-TNF- α therapy have also raised concerns that patients may exhibit reduced sensitivity when retreated with the anti-TNF- α agent after disease recurrence.^{41,43} There are no published data addressing the safety of stopping adalimumab from an ocular standpoint, especially concerning development of reduced efficacy of anti-TNF- α therapy in the eye.

As the use of biologics in uveitis becomes increasingly common, questions regarding the safe and efficient use of anti-TNF- α therapy become increasingly relevant. In this multicenter, observer-masked, randomized clinical trial, we will compare rates of reactivation of ocular inflammation and adverse events

in patients with JIA-associated uveitis or CAU randomized to either continue their current treatment regimen of adalimumab or discontinue adalimumab. Addressing these clinically relevant research aims will provide a stronger evidence base for informing treatment guidelines for long-term use of adalimumab in patients with JIA-associated uveitis and CAU.

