Patients in the placebo arm will be encouraged to restart adalimumab. The date of treatment failure is defined as the date of the initial visit when the ocular inflammation reached the threshold. A minimum of 90 days of follow-up is required following treatment failure, so if treatment failure is declared with fewer than 90 days remaining in the 12-month follow-up period, follow-up may be extended to up to 15 months. Regardless of the course of treatment pursued after treatment failure, all patients will be followed through Month 12 or a minimum of 90 days, whichever is longer.

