6.1.2 DOSING AND ADMINISTRATION

The participant's dose will be selected based on their current weight at the time of randomization. For example, a patient weighing less than 30kg who is randomized to continue adalimumab treatment will receive a dose of 20mg every other week for up to 12 months. If a patient's weight increases during the trial, the patient must hold the larger weight for two consecutive visits (≥ 28 days apart) before receiving the higher dose of adalimumab (i.e. 40mg biweekly).

Participants randomized to receive placebo treatment will receive a volume-matched placebo dose subcutaneously every other week for up to 12 months.

Patients will take their first dose of study treatment 14 days after their most recent injection prior to entering the trial. Patients in either arm may discontinue treatment at any time for safety, intolerance, or efficacy. Further information on safety, intolerance, and efficacy definitions are provided in **Section 7.1**. After discontinuing treatment, such patients would be treated per best medical judgement and continue to be followed in the study until the completion of the Month 12 visit. If treatment failure is declared with fewer than 90 days left in the 12-month follow-up period, follow-up should be extended up to 15 months. Patients in the placebo arm may restart adalimumab during the study. Patients in the adalimumab arm may continue on adalimumab. The study will provide open-label adalimumab treatment for all patients who restart, regardless of their randomization arm. The advised dose for

restarting adalimumab will be 40mg every other week for patients $\geq 30\text{kg}$ or 20mg every other week for patients $< 30\text{kg}$.

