8.3.4 TIME PERIOD AND FREQUENCY FOR EVENT ASSESSMENT AND FOLLOW-UP

The occurrence of an AE or SAE (encompassing serious adverse reactions, SARs, and suspected unexpected serious adverse reactions, SUSARs, in the UK) may come to the attention of study personnel during study visits and interviews of a study participant presenting for medical care, or upon review by a study monitor.

All AEs including local and systemic reactions will be captured on **Adverse Event Checklist**. All AEs that occur during the study must be documented appropriately regardless of relationship and will be categorized as either serious or non-serious. All AEs will be followed to adequate resolution.

Any medical condition present at the time that the participant is screened will be considered as baseline and not reported as an AE. However, if the study participant's condition deteriorates at any time during the study, it will be recorded as an AE.

The study coordinator will record all reportable events with start dates occurring any time after informed consent is obtained until 70 days after the last day of study participation and the last dose of study medication. At each study visit, the study coordinator will ask about the occurrence of AE/SAEs

since the last visit. Events will be recorded on **Adverse Event Checklist** at each visit and followed for outcome information until resolution or stabilization.

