7.1 Exposure

Individuals are assumed to have exposure to the intervention corresponding to the group to which they were randomized.

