7.2 Adverse Events

7.2.1 Individual Events

Adverse event reporting procedures are described fully in Protocol Section 8.3.² Non-serious adverse events are described in Protocol Section 8.3.1.² Serious non-ocular or ocular adverse events (which must be reported within 24 hours and which require a narrative form) are described in Protocol Section 8.3.2.² Adverse events will be reported in all presentations and publications.

Safety-related events that occurred at or before treatment failure with censoring at 6 months and then 12 months (two different groups of safety-related events) will be tabulated and reported. Descriptive tables of the number and frequency of adverse events will be broken down by treatment group, age, sex, antimetabolite use and known comorbidities. We will report total adverse events and serious adverse events, cross-tabulated by whether the adverse events were anticipated or unanticipated and by whether or not the adverse event led to discontinuation of medication.

We do not propose statistical evaluation of adverse events, since the study is not powered for such assessments.

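### The SAP does not say whether adverse events after treatment failure or in the 70-day period enter its safety tables, and its as-randomized exposure rule would count events on restarted adalimumab under placebo

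*SAP*

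**What the plan says.** **Collection.** Protocol 8.3.4 records events from consent "until 70 days after the last day of study participation and the last dose of study medication". Footnote f of the assessment schedule in Protocol 1.3 adds an AE call: "Patients are contacted approximately 70 days after their last study visit". The visit table in the same section places that call at week 58 from baseline, with a window of more than 56 to 60 weeks.

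**After failure.** Protocol 3.1 states that "all patients will be followed through Month 12 or a minimum of 90 days, whichever is longer", with extension up to 15 months. Protocol 4.4 requires an AE report at the 90-day post-failure visit. Protocol 6.1.2 says: "The study will provide open-label adalimumab treatment for all patients who restart, regardless of their randomization arm".

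**Reporting.** SAP 7.2.1 will tabulate "Safety-related events that occurred at or before treatment failure with censoring at 6 months and then 12 months". It continues: "Descriptive tables of the number and frequency of adverse events will be broken down by treatment group, age, sex, antimetabolite use and known comorbidities", and then plans a report of total AEs and SAEs. SAP 7.2.2 adds six pooled proportions (ocular, systemic and laboratory, each for AEs and SAEs). None of these later items states a window. SAP 7.1 sets the exposure rule: "Individuals are assumed to have exposure to the intervention corresponding to the group to which they were randomized".

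**The concern.** The strategy under test in the stop arm is to stop and, for many patients, to fail and restart. The protocol collects AEs through all of that and beyond. The SAP's one stated window covers only the part before failure, and its other AE tables leave the period open.

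Two analysts could build different safety tables from this text. One would carry the failure cut through all of 7.2 and drop every event on restarted drug. The other would include all collected events and, under 7.1, place an infection or laboratory event on restarted adalimumab in the placebo column. The protocol hypothesizes a higher AE rate with continued treatment (4.1), so the second reading would blur the contrast of interest, and the first would describe only the pre-failure part of the stop strategy. Neither gives a count of events during re-treatment.

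**Working it through.** **Step 1: the three safety texts set side by side.**

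| Item | Window stated | Stop-arm event on restarted adalimumab |
|---|---|---|
| 7.2.1, first tabulation | To failure, cut at 6 and 12 months | Omitted |
| 7.2.1 breakdowns and totals; 7.2.2 proportions | None | Omitted if the cut carries over; otherwise counted under placebo by 7.1 |
| Any table by drug received after failure | Not planned | – |

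Events in the 70-day period of a patient who never fails come after the 12-month cut, so the first tabulation omits them; the other tables do not say.

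**Step 2: inputs for size.** SAP 3.3.1 gives medians of 10 weeks (stop) and 20 weeks (continue), 59 per arm, 10% loss, two-sided alpha 0.05 and a hazard ratio of 2.0. Follow-up is 48 weeks (Protocol 1.1). Failure times are taken as exponential, as in the SAP's formula, with rate λ = ln 2 / median: 0.06931 and 0.03466 per week.

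**Step 3: reproduce the SAP's power.** With φ(λ) = λ²/(1 − e^(−48λ)), φ is 0.004983 and 0.001482, sum 0.006465. The squared rate difference is 0.001201. With 59 × 0.9 = 53.1 per arm, z = √(53.1 × 0.001201/0.006465) − 1.960 = 1.181, a power of 88.1%. The SAP states 88%, so the inputs are read correctly.

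**Step 4: time inside the stated window.** Probability of failure by week 48 is F = 1 − e^(−48λ). Mean time to failure or week 48, over all patients in the arm, is F/λ.

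- Stop: F = 0.964; 0.964/0.06931 = 13.9 weeks inside; 34.1/48 = 71% after failure.
- Continue: F = 0.811; 0.811/0.03466 = 23.4 weeks inside; 24.6/48 = 51% after failure.

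Adding the 90-day minimum after failure and 10 weeks for the 70-day period, 76% (stop) and 60% (continue) of AE collection time lies after the window.

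**Step 5: sensitivity.** SAP 3.3.1 calls the 20-week median conservative and cites adult data with over 90% inactive at week 54 and 74% at week 78. It also cites about 80% recurrence within a year of stopping. Taking 80%, and 10% or 26%, as 48-week failure risks is an assumption; then λ = −ln(1 − F)/48.

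| Arm and assumed F | Weeks inside | Share of 48 weeks after failure |
|---|---|---|
| Stop, 80% | 23.9 | 50% |
| Continue, 10% | 45.6 | 5% |
| Continue, 26% | 41.4 | 14% |

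Loss to follow-up, ignored in steps 4 and 5, would lower the shares slightly.

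**Step 6: the AE call.** Week 58 equals 48 + 10, which fits a last visit at week 48. A patient failing at week 48 has a 90-day visit at 48 + 12.9 = week 60.9, already past week 58; ten weeks later is week 70.9. Failures after week 48 − 12.9 = 35.1 are affected. At the design medians that is 59 × (0.0875 − 0.0359) + 59 × (0.2959 − 0.1895) = 3.0 + 6.3, about 9 of the planned 118.

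**The case against.** A reader might infer that post-failure events are not reported at all. The documents do not support that. The totals and breakdowns in SAP 7.2.1, the pooled proportions in 7.2.2 and the summary of deaths in section 7 have no cut at failure. The safety population in SAP 4.1 is everyone who received the intervention. DSMC reports list all adverse outcomes (SAP 6.2.2). Aim 3 summarizes discontinuation for safety and for intolerance by 6 and 12 months regardless of treatment changes after failure. Silence about a window is not exclusion, and this part of the objection stands.

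A reader might also take the protocol's re-treatment concern as a warning of hypersensitivity on re-exposure. The Background says that "patients may exhibit reduced sensitivity when retreated with the anti-TNF- α agent after disease recurrence", which is loss of efficacy. The SAP studies that through time to regaining control and antibody levels. Hypersensitivity is listed in Protocol 2.3.1 only as a general adalimumab risk.

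Nor is all post-failure time re-treatment time. Failure is dated to the first visit at threshold, while for the sustained-inflammation criteria unmasking follows confirmation at 7 or 28 days. Some patients will not restart. The 51% for the continue arm rests on a median that the SAP itself calls conservative.

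What the objection does not remove is the choice that each table without a stated window leaves open: omit the restart event, or count it under placebo. The other summaries do not settle this, because none presents AEs by drug received after failure.

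**Conclusion.** The point holds as an unresolved window and a misattribution, not as lost data. The SAP gives one AE window that ends at failure or Month 12, leaves its other AE tables without one, and fixes exposure as randomized. Under either reading, no planned table shows AEs on restarted adalimumab as such.

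The follow-up at issue is about 71% (stop) and 51% (continue) of the 48 weeks at the design medians, or about 50% and 5% to 14% under the assumed lower failure risks. These figures rest on exponential failure times and complete follow-up, and measure time after failure, not time on restarted drug. All re-treatment following failure lies outside the stated window in every case.

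The primary efficacy analysis is unaffected. The safety tables are descriptive, so the consequence is for what readers can learn about the stop-and-restart course. It should be corrected. The timing of the AE call is a separate, smaller inconsistency within Protocol 1.3.

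**What to change.** 1. Keep the pre-failure table in SAP 7.2.1.
2. State the start and end of the window for every other table in 7.2.1 and 7.2.2.
3. Add one descriptive table of AEs, SAEs and laboratory AEs from treatment failure to the end of AE collection (70 days after the last day of participation and the last dose). Group it by drug actually received after failure, taken from the Treatment Assessment Forms. Give the number of patients who restarted and the person-time in each group.
4. Amend SAP 7.1 so that this table uses actual exposure; the as-randomized rule can stay for the others.
5. State where 70-day events are reported for patients who never fail.
6. In Protocol 1.3, reconcile the fixed week-58 AE call with footnote f for patients followed beyond Month 12.

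Items 1 to 5 cost SAP wording, one extra table and the linking of AE and treatment forms. No new visit or hypothesis test is needed. Person-time assumes that the treatment forms hold restart and stop dates, which the documents do not show field by field.

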4 STUDY DESIGN

4.1 OVERALL DESIGN

Hypotheses for this trial include:

- 1) Patients who stop adalimumab will have a shorter time to uveitis recurrence compared to those who continue treatment. Patients randomized to continue treatment will have a higher rate of adverse events compared to patients randomized to stop treatment.
- 2) Patients with higher serum levels of MRP8/14, higher ESR, higher ADA, and higher CRP will have a higher uveitis recurrence rate compared to patients with lower serum levels. In addition, period of inactive uveitis, age at randomization, and duration of adalimumab treatment before randomization will be associated with uveitis recurrence rate.
- 3) A smaller proportion of patients who stop adalimumab will have controlled ocular inflammation at Month 6 and Month 12 compared with patients who never stop adalimumab. In addition, among patients who stop adalimumab and have a uveitis recurrence, anti-adalimumab antibodies will be associated with a longer time to regaining uveitis control after restarting treatment. MRP8/14 levels will be associated with the likelihood of establishing control of ocular inflammation after restarting adalimumab treatment following uveitis recurrence.

This study is a phase IV clinical trial.

The study design is a multicenter, randomized, placebo-controlled, superiority trial comparing stopping adalimumab treatment to continuing adalimumab treatment for patients with JIA-associated uveitis or CAU who have achieved corticosteroid-sparing control of inflammation on 12 consecutive months of adalimumab or a biosimilar treatment. Patients randomized to continue adalimumab treatment will receive the standard clinical practice weight-based dose of adalimumab. Patients in both arms will remain on their current dose of concomitant antimetabolite therapy if applicable. Further detail on dosing and administration of study treatment is provided in **Section 6.1.2**.

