Randomization will be stratified by use of concomitant antimetabolite therapy and by country. Patients will be treated as originally randomized until treatment failure is declared, at which point, they may be treated per best medical judgement. The primary outcome will be time to treatment failure (as defined in **Section 3** primary endpoint) up to 12 months post-randomization. Rates of disease recurrence and rates of adverse events will also be compared between the two treatment groups. All patients will be followed through Month 12 for the purpose of obtaining secondary, long-term clinical outcome data.

Patients originally randomized to stop adalimumab treatment who experience a treatment failure may restart adalimumab treatment during the trial and will be assessed at Month 12. Primary outcome analysis will be intent-to-treat, but a secondary per-protocol analysis will be performed, and subgroup analyses will be performed on patients who stop and restart adalimumab treatment. Further detail on statistical analysis is provided in **Section 9.4**.

MRP8/14 serum levels, ESR, CRP, and adalimumab antibody levels will also be measured periodically during the trial. These biomarkers will be assessed as potential predictors for disease recurrence in patients with JIA-associated uveitis or CAU.

The trial will have 10 enrollment centers in the U.S., 9 in the UK, and 1 in Australia. Additional sites may be added during the study to facilitate enrollment. U.S. study sites will include the F.I. Proctor

Foundation at University of California San Francisco (UCSF), Children's Hospital of Philadelphia, Cincinnati Children's Hospital, Children's Mercy Hospital in Kansas City, MO, University of Utah Health in Salt Lake City, Colorado Retina Associates in Lakewood, CO, University of California Davis Eye Center in Sacramento, CA, Vanderbilt Eye Institute in Nashville, TN, University of Texas in Austin, TX, and University of Miami, FL. UK study sites will include Great Ormond Street Hospital in London, University Hospitals Bristol, Alder Hey Children's Hospital in Liverpool, Great North Children's Hospital in Newcastle, Sheffield Children's Hospital, Cambridge University Hospital, Royal Manchester Children's Hospital, University Hospital of Leicester, and Norfolk and Norwich University Hospital. The Australian study site is The Royal Children's Hospital in Melbourne.

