4.2 SCIENTIFIC RATIONALE FOR STUDY DESIGN

Justification for placebo treatment: As both patients and those assessing outcomes could introduce bias, complete masking of the treatment is ideal for this study. This concern is especially pertinent for the pediatric population, since it is difficult to prevent young patients from discussing their treatment with their physician. Our primary outcome is time to treatment failure, where treatment failure is defined as a recurrence of ocular inflammation (≥ 2 -step increase in AC cell observed at 2 consecutive visits at least 7 days apart; $>0.5+$ AC cell for ≥ 28 days; $\geq 3+$ AC cell observed at a single visit; or $>0.5+$ vitreous haze, active retinal/choroidal lesions, or macular edema at a single visit) and/or a recurrence of joint inflammation that is persistent and severe enough to necessitate unmasking to manage the arthritis recurrence. While an attempt will be made to ensure the grading of ocular inflammation is as standardized as possible, complete removal of subjectivity in inflammation grading is impossible. Furthermore, we plan to assess adverse events and quality of life as secondary outcomes, which rely on patient self-report. Given that self-report is involved in both the primary and secondary outcome assessments, masking of subjects is also necessary to remove any potential bias in assessing the outcomes for our study.

Justification for superiority: There is clinical utility in determining if one treatment plan is more effective for reducing the risk of recurrence of ocular inflammation. The findings of this trial could provide justification for either stopping adalimumab or continuing adalimumab for long-term management of JIA-associated uveitis and CAU, which are chronic conditions. Therefore, a superiority trial design is warranted.

Potential problems with placebo treatment: We hypothesize that stopping adalimumab will result in a shorter time to treatment failure and higher uveitis recurrence rates compared to continuing adalimumab. In anticipation of this possibility, we have allowed for patients to restart adalimumab or be treated per best medical judgement for the remainder of the study period. The primary analysis will be intent-to-treat, but we will also collect clinical outcome data at Month 12 to assess whether the initial strategy of stopping treatment results in worse outcomes compared to the initial strategy of continuing therapy.

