3.5 Multiple comparisons

No multiple comparison corrections will be made. All analyses following the primary analysis for each of the three Aims will be reported as descriptive and will be presented with 95% confidence intervals.

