7.2.2 Pooled adverse events

Adverse events will be analyzed according to six main categories:

- Proportion of subjects with any ocular adverse event
- Proportion of subjects with any ocular serious adverse event
- Proportion of subjects with any systemic adverse event
- Proportion of subjects with any systemic serious adverse event
- Proportion of subjects with any laboratory adverse events
- Proportion of subjects with any laboratory serious adverse events

Note, hypothesis tests based on adverse events may be less than useful because the trial is not powered for these comparisons. These will only be provided to the DSMC if requested.

8 Reporting conventions

- All tables, data listings and figures will be presented in landscape orientation
- Direct annotation of figures will be preferred to legends. All figures with more than one variable or item will contain direct annotation
- Color will be used in figures only when needed to enhance clarity of communication

9 Appendix

All computations will be performed using the R statistical software ([R Core Team 2021](#)).³⁹ Specification of the random number seed and pseudorandom number algorithm determines the entire randomization assignment. Accordingly, the random number seed will be kept confidential.

10 References

2. [name]. *Adalimumab in Juvenile Idiopathic Arthritis-Associated Uveitis Stopping Trial (ADJUST)*.; 2019.

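### The protocol promises a comparison of adverse-event rates, but the SAP plans only by-arm tables up to treatment failure, with no contrast, interval or person-time denominator

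*SAP*

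**What the plan says.** The second sentence of Hypothesis 1 in Protocol 4.1 reads: "Patients randomized to continue treatment will have a higher rate of adverse events compared to patients randomized to stop treatment". The same section adds: "Rates of disease recurrence and rates of adverse events will also be compared between the two treatment groups". Protocol 4.2 counts adverse events among the secondary outcomes: "we plan to assess adverse events and quality of life as secondary outcomes, which rely on patient self-report". Protocol sections 3 and 9 leave the endpoints and all statistics to the SAP.

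SAP 7.2.1 plans tabulation by arm: "Descriptive tables of the number and frequency of adverse events will be broken down by treatment group, age, sex, antimetabolite use and known comorbidities". The events tabulated are those at or before treatment failure, censored at 6 and then at 12 months. The section ends: "We do not propose statistical evaluation of adverse events, since the study is not powered for such assessments". SAP 7.2.2 goes a little further: "Adverse events will be analyzed according to six main categories". These are proportions of subjects with any ocular, systemic or laboratory event, each for all events and for serious ones. On hypothesis tests it says: "These will only be provided to the DSMC if requested". SAP 3.7 also describes adverse-event reporting as descriptive.

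Outside section 7, the SAP compares discontinuation for intolerance and for safety between arms (2.3.3 and 3.1.3). SAP 4.2 applies Fisher's exact test to the proportion and reason for discontinuation.

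**The concern.** A stated, directional hypothesis has no analysis that can answer it. The SAP's reason is lack of power. That is a reason not to test or to lean on a P value. It does not prevent an estimated contrast with its interval, which would show the reader what size of difference the data leave open.

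The missing denominator matters more. The protocol's hypothesis is about a rate, while SAP section 7 plans numbers, frequencies and proportions of subjects. If one arm fails sooner, its patients are observed for less time before the count stops, so they accumulate fewer events whatever the drug does. The trial's own efficacy hypothesis is that the stop arm fails sooner. The tables are therefore tilted towards the adverse-event hypothesis by design. Concern about long-term adverse events is one of the reasons given for studying withdrawal (Protocol 2.1 and 2.2), so this is a comparison that readers will look for.

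**Working it through.** **Inputs.** From SAP 3.3.1: 59 patients per arm, 88% power, hazard ratio 2.0, two-sided alpha 0.05, 10% loss, median time to failure 10 weeks (stop) and 20 weeks (continue). Follow-up is 48 weeks (Protocol 1.1). The documents give no adverse-event rate, so a range is assumed below.

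**1. The plan's own figure.** With λ = ln 2 / median, λ is 0.0693 per week (stop) and 0.0347 (continue). With φ(λ) = λ²/(1 − e^(−λT)) and T = 48, the SAP formula gives

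N per arm = (1.960 + 1.175)² × (φ(0.0693) + φ(0.0347)) / (0.0693 − 0.0347)² = 52.9.

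That is 105.8 in total, and 105.8 / 0.90 = 117.6, i.e. 118. The sample size is reproduced, so the planning inputs are read correctly. No stated figure is wrong.

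**2. Time at risk up to failure.** Mean time = (1 − e^(−λT))/λ.

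- Stop: (1 − e^(−3.327))/0.0693 = 13.9 weeks
- Continue: (1 − e^(−1.664))/0.0347 = 23.4 weeks
- Ratio: 23.39 / 13.91 = 1.68

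Adding the SAP appendix's dropout rate of 0.0022 per week gives 13.5 and 22.5 weeks, ratio 1.66. If both arms have the same true event rate, expected counts up to failure have this same ratio.

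**3. Proportion with any event before failure, same true rate r in both arms.** P = r/(r + λ) × (1 − e^(−(r + λ)T)).

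| Assumed r per week | Stop | Continue |
|---|---|---|
| 0.01 | 12% | 20% |
| 0.02 | 22% | 34% |
| 0.05 | 42% | 58% |
| 0.10 | 59% | 74% |

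The six proportions in SAP 7.2.2 carry the same distortion if they use the window in 7.2.1. A plain risk difference would put a confidence interval around it without removing it.

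**4. Precision of a contrast at 59 per arm.** The half-width for a difference in proportions is 1.96 × √(2p(1 − p)/59): 7.9 points at p = 5%, 10.8 at 10%, 14.4 at 20%, 16.5 at 30% or 70%, and 18.0 at 50%. At 53 per arm (after 10% loss) the range is 8.3 to 19.0 points.

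For a rate ratio under a Poisson model the interval is a factor exp(1.96 × √(1/e₁ + 1/e₂)) either way. At an assumed 1 event per patient-year, e₁ = 59 × 13.9/52.18 = 15.7 and e₂ = 26.4, so the factor is 1.87. At 4 per patient-year (62.9 and 105.8 events) it is 1.37. Clustering of events within patients would widen both.

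**5. The power argument.** At 59 per arm, the difference in adverse-event proportions detectable with 80% power is about 18 to 25 points over the same range of p. SAP 3.3.2 accepts 28 points for uveitis flares, 26 for JADAS-10 improvement, and 28 to 29 for Aim 3 control.

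**The case against.** Descriptive safety reporting in a trial of this size is a defensible and common choice, and here it is deliberate: SAP 3.7 and SAP 7.2.1 both say so. The protocol defers statistics to the SAP, its word for the comparison names no model, and a by-arm table is a form of comparison. The gravest harms named in Protocol 2.2, malignancy and opportunistic infection, are ones on which a 12-month interval from about 59 patients per arm says little. Stopping the count at failure is also sensible, because stop-arm patients may restart adalimumab afterwards.

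Most of this stands. It argues against tests and against over-reading. It does not explain why the hypothesised rate has no denominator, and a deliberate descriptive choice can still produce a misleading table when time at risk differs by arm.

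Three stronger readings are tempting, and the documents do not support them.

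- A reader might infer that the SAP refuses any between-arm safety evaluation. It does not: events are tabulated by arm, six proportions are planned, and discontinuation is compared between arms.
- A reader might infer that SAP 3.5 promises intervals for everything except adverse events. Its statement that results "will be presented with 95% confidence intervals" applies to analyses that follow the primary analysis of each of the three Aims. Adverse-event rates are not among the outcomes listed for any Aim. If 3.5 were nonetheless read to include them, an interval would already be promised, but still without a named contrast.
- A reader might take the protocol to claim causation, or the rationale for stopping to rest on adverse events alone. The protocol says only that the rate will be higher, and Protocol 2.1 also cites cost and possible drug resistance.

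**Conclusion.** The point holds in this form: the protocol promises a comparison of adverse-event rates, and the SAP supplies by-arm tables and proportions with no contrast, interval or person-time. Under the SAP's planning medians the tables would show about 1.7 times as many events in the continue arm with no true difference in rate.

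That figure assumes exponential failure times, a constant adverse-event rate and 48 weeks of potential follow-up. The percentages with any event also depend on assumed event rates. The real gap depends on observed failure times, which the documents do not give. SAP 3.3.1 calls the 20-week median conservative, and the version 5 revision note says the treatment effect was much larger than anticipated, so 1.7 illustrates the problem and does not predict its size. If the stop-arm median were 10 weeks and nobody in the continue arm failed, the ratio would be 48/13.9 = 3.5. Longer times to failure in both arms would shrink it.

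Nothing here touches the primary efficacy analysis or shows that any reported safety result is wrong.

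**What to change.** Replace the last sentence of SAP 7.2.1 with wording along these lines: rate ratios (continue versus stop) for adverse events and for serious adverse events will be reported descriptively, with 95% confidence intervals and no P values. They will come from a negative binomial or robust Poisson model with log person-time to failure as offset, and country and antimetabolite use as covariates where event counts allow.

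For the six categories in SAP 7.2.2, give exposure-adjusted incidence rates by arm with a rate ratio or rate difference and its 95% interval. Unadjusted risk differences should not stand alone.

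Name this as the analysis of the adverse-event part of Protocol Hypothesis 1. Version 5 of the SAP was written after unmasking at the interim, so label the addition as made after that point.

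The cost is a short SAP edit and a few models on data already collected. The downside is wide intervals, especially for serious events. At the planned 59 per arm the half-width for a difference in proportions is about 8 to 18 points (event proportions of 5% to 70% assumed), and it would be wider if the early stop of enrollment left fewer patients per arm.
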